8.5 Analyses Plans

Data will be summarized with respect to demographic and baseline characteristics and safety observations and measurements. The assessment of safety will include calculation of all specified study endpoints (see section 8.2) and will be based mainly on the frequency and attribution of adverse events, the frequency of discontinuation of treatment due to toxicity during concurrent vismodegib plus radiation therapy, and the proportion of patients experiencing Grade

3 or higher AEs related to the treatment components. Adverse events will be summarized by presenting the number and percentage of patients having any adverse event. Any other information collected (e.g. severity or relatedness to study medication) will be listed as appropriate. Toxicities will be tabulated by maximum grade occurring and organ system using the NCI Common Toxicity Criteria version 4.1 during each of 4 protocol stages (vismodegib alone, in combination with radiation therapy, during the immediate 3 months following completion of protocol therapy and then up to 12 months of follow-up after completing treatment).

To evaluate the primary protocol aim the proportion of patients with local-regional control (LRC), those with a CR or PR as defined by RECIST criteria, at 12 months after completing protocol therapy will be calculated and presented with 95% confidence intervals. As a most conservative estimate of disease control any patient beginning concurrent vismodegib and radiation therapy who is removed from study prior to completion of at least 75% of radiation therapy without a documented complete or partial response will be considered as a local-regional failure. To test the primary study hypothesis the observed proportion with LRC will be compared with the null hypothesis of 60% using a one sample test of a binomial proportion.

The secondary clinical aims of the duration of progression free survival (PFS) and overall survival (OS) will be measured from the start of protocol therapy until death due to any cause or until the first evidence of any disease progression, or death, respectively. Point estimates (e.g. median, percent PFS at 12 months) with 95% confidence intervals will be calculated using the Kaplan-Meier product limit method to summarize results. Based upon RECIST criteria, the proportion of patients responding in the primary site and regionally involved areas at 3 months after completing protocol therapy will be determined and presented with 95% confidence intervals. The proportion of patients achieving any decrease in BCC within the boundaries of the treated radiation PTV area will be determined and presented with a 95% confidence interval. In addition, the proportion of patients who start concurrent vismodegib and radiation therapy and receive at least 75% of the planned radiation therapy will be determined and presented with a 95% confidence interval to summarize the feasibility of administering concomitant therapy.

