Secondary Objectives	
 • To estimate of the probability of PFS, with failure defined as any disease recurrence or death due to any cause, and OS with the duration for each measured from the time of first treatment with vismodegib to 12 months after completion of study treatment. • To evaluate toxicity during the drug-alone and combined-modality components of the protocol regimen during treatment. This will be assessed by: 
 1) The number and attribution of all adverse events, (including vital signs, physical findings, and clinical laboratory results, CTCAE, v 4.0) in patients who receive any amount of study drug and radiation therapy. 2) The proportion of any adverse events (CTCAE, v. 4.0) assessed to be definitely, probably, or possibly related to vismodegib or its combination with radiation therapy. 3) The proportion of patients experiencing Grade 4-5 adverse events assessed to be definitely, probably, or possibly related to the induction or concurrent treatment components of the protocol regimen (that is not definitely related to disease progression). • To evaluate initial toxicity during the 3 months immediately after completion of protocol therapy. • To estimate the feasibility of administering concurrent vismodegib with radiation therapy determined by the proportion of patients discontinuing treatment due to toxicity during the concurrent administration of vismodegib and radiation therapy (<75% of planned radiation therapy delivered). • To evaluate the response rate (as per RECIST version 1.1) of the primary site and regionally involved areas following all treatment components at 3 months after the completion of protocol therapy. • To estimate the clinical response to vismodegib and radiation therapy determined by the proportion of patients with a decrease of BCC within the irradiated planning tumor volumes (PTVs, see Section 5.0 for definition) in patients who complete combined therapy.

Study Design	This is a single arm, multi-centered Phase II clinical trial to assess the safety and demonstrate the efficacy of a combined modality approach using radiation therapy after induction and concurrently with systemic administration of vismodegib, which may increase the rates of complete response and sustained local control in patients with locally advanced BCC.
Number of patients	24 evaluable patients who complete at least 75% of protocol-mandated radiotherapy.

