3.2 Number of Subjects

Required Sample Size: 24 evaluable patients who complete at least 75% of protocol-mandated radiotherapy. Patients who withdraw consent, drop out of the study before starting radiation therapy or before completing 75% of protocol treatment without grade ≥ 3 toxicity will be replaced. Any patient receiving any study drug will be included in the analysis of toxicity.

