6.1.2.2 Study Procedures, Week 13-14 (End of Induction)

Within 14 days after completion of induction vismodegib therapy, patients must have a re-evaluation to determine if there has been disease progression prior to starting concurrent treatment. Patients whose disease has progressed will no longer continue on study.

- Physical examination including weight
- Vital signs
- Performance status
- Evaluation of adverse events
- Concomitant medications
- Skindex-16 survey
- Laboratory assessments
 - Hematology
 - Serum chemistries
- Urine or serum pregnancy tests - if a woman of childbearing age
- Disease assessment
- Imaging (CT or MRI) of head and neck for tumor assessment
- CT chest or chest x-ray – if clinically indicated
- For externally visible tumors
 - Bidimensional measurements of externally visible tumor dimension
 - Standardized digital photography of target lesion(s)

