7.2.1.1 Definitions

Evaluable for toxicity

All patients receiving any study drug will be evaluable for toxicity from the time of their first treatment with the study drug.

Evaluable for objective response

Only those patients who have measurable disease present at baseline, have completed at least 75% of protocol-mandated radiotherapy, and have had their disease re-evaluated will be considered evaluable for response. These patients will have their response classified according to the definitions stated below. (Note: Patients who exhibit objective disease progression prior to the end of induction therapy will also be considered evaluable.)

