8.3.2 Replacement Policy

Patients who drop-out before starting radiation therapy will be replaced. In addition, patients who come off study before completing at least 75% of radiation therapy given concurrently with vismodegib without grade ≥ 3 toxicity will be replaced. The frequency of each of these events will be reported and reasons for replacement reviewed.

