8.5.1 Analysis Population

The statistical analysis of efficacy will include all patients completing the initial treatment with vismodegib alone and start the concurrent vismodegib with radiation therapy. Anyone who receives any vismodegib with radiation therapy will be included in the assessment of efficacy. As the most conservative approach, any patient removed from study prior to completion of at least 75% of radiation therapy without a documented complete or partial response will be considered as a case of local-regional failure.

Failure is defined as a lack of local-regional control within the boundaries of the treated radiation PTV area within the 12 month follow-up period.

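### The early-removal failure rule is waived by an undated response, some exits have no stated result, and the analysed set conflicts with the set the trial is sized on

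*Combined protocol and SAP*

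**What the plan says.** **Endpoint.** Sections 8.2 and 8.5 define success as CR or PR, with no progression inside the irradiated PTV, 12 months after protocol therapy ends. Section 8.5 tests the proportion against 60%.

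**Early removals.** Sections 8.5 and 8.5.1 both count as a failure a patient who started concurrent therapy and was "removed from study prior to completion of at least 75% of radiation therapy without a documented complete or partial response". Both present this as the most cautious choice.

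**General failure definition (8.5.1).** "Failure is defined as a lack of local-regional control within the boundaries of the treated radiation PTV area within the 12 month follow-up period".

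**Who is counted.** The sections differ:
- 8.5.1: "Anyone who receives any vismodegib with radiation therapy will be included in the assessment of efficacy".
- Abstract and 3.2: the required size is "24 evaluable patients who complete at least 75% of protocol-mandated radiotherapy".
- 7.2.1.1: only patients with measurable disease who "have completed at least 75% of protocol-mandated radiotherapy, and have had their disease re-evaluated will be considered evaluable for response"; a note adds patients who progress during induction.
- 3.2: patients who "drop out of the study before starting radiation therapy or before completing 75% of protocol treatment" are replaced if they had no grade 3 or higher toxicity. Section 8.3.2 likewise replaces "patients who come off study before completing at least 75% of radiation therapy given concurrently with vismodegib" without such toxicity, and also anyone who leaves before radiation starts.

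**Assessment timing.** Section 6.1.2.2: "Within 14 days after completion of induction vismodegib therapy, patients must have a re-evaluation". Table 6.1 shows no disease assessment during radiation; the next one is at weeks 29-33.

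**The concern.** A rule meant to be cautious should not depend on a response seen before the treatment under test has been given. As worded, a partial response to vismodegib alone could lift a patient out of automatic failure, and nothing then says how that patient is scored if no 12-month assessment exists. Section 1.2.2 reports response rates of 43% (independent review) and 60% (investigator) in locally advanced disease on the drug alone. That trial dosed until progression, so the rate after 12 weeks is unknown, but induction responses need not be rare.

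Separately, a patient who starts concurrent therapy, leaves before 75% of radiotherapy and is replaced belongs to the efficacy set of 8.5.1 but not to the 24 evaluable patients. The plan expects such exits: it has a replacement policy, and 8.4 accepts 2 of the first 5 patients stopping before 75%. In an open single-arm trial without central imaging review, the reading could be chosen after outcomes are known.

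**Working it through.** **1. The plan's own figure (8.3.1).** Inputs: N = 24, null 0.60, alternative 0.80, one-sided 0.10, exact binomial. The smallest passing count is 18:
- P(X ≥ 17 | 24, 0.60) = 0.192, above 0.10.
- P(X ≥ 18 | 24, 0.60) = 0.096, the exact alpha.
- P(X ≥ 18 | 24, 0.80) = 0.811, against 81% stated. The sample-size calculation reproduces.

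**2. Which response can be on file at an early removal.** Radiation is 33-35 fractions at 5 per week from week 15. The 75% mark is 0.75 × 33 = 24.75 to 0.75 × 35 = 26.25 fractions, or 4.95 to 5.25 weeks, so it is reached around weeks 19-20. Between baseline and that point the only scheduled disease assessment is the end-of-induction one at weeks 13-14. A response seen there could in practice be only a PR, because CR under 7.2.1.4 needs two observations at least 4 weeks apart. Section 7.2.1.4 also words PR in terms of lesions in the irradiated PTV, so whether an induction PR qualifies is itself unclear.

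**3. Exits set against the rules.**
- Progression inside the PTV: failure under 8.5.1.
- Salvage surgery after biopsy-proven persistent cancer (6.1.3): arguably failure under 8.5.1, but not written.
- Removal before 75%, no CR/PR documented: failure.
- Removal before 75%, CR/PR documented, no 12-month assessment: no result stated.
- Missing 12-month assessment for another reason: no result stated.
- Non-protocol treatment to the treated site, or an off-protocol Hedgehog inhibitor or chemotherapy (6.1.5), without local progression: no result stated.

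**4. Effect of the denominator.** The documents give no exit counts, so these are assumed. Suppose 18 of 24 evaluable patients are controlled and replaced failures had started concurrent therapy:
- None: 18/24 = 75.0%, p = 0.096, passes.
- One kept: 18/25 = 72.0%, p = P(X ≥ 18 | 25, 0.60) = 0.154, fails.
- Two kept: 18/26 = 69.2%, p = P(X ≥ 18 | 26, 0.60) = 0.226, fails.

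**5. Cut-offs for the N actually analysed.** The smallest count with exact alpha at or below 0.10:
- N = 24: 18, alpha 0.096.
- N = 25: 19, alpha 0.074.
- N = 26: 20, alpha 0.056.

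**6. Power under strict coding.** One or two patients are certain failures, the others are controlled at 80%, N = 24, cut-off 18:
- One: P(X ≥ 18 | 23, 0.80) = 0.695.
- Two: P(X ≥ 18 | 22, 0.80) = 0.543.

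If they are also replaced and kept:
- One, N = 25: P(X ≥ 19 | 24, 0.80) = 0.656.
- Two, N = 26: P(X ≥ 20 | 24, 0.80) = 0.460.

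**The case against.** **The endpoint already governs.** Success requires CR or PR at 12 months, so escaping automatic failure is not success. This stands. A reader might infer that a waived patient is credited as controlled; scoring one or two of 24 that way would raise alpha from 0.096 to P(X ≥ 17 | 23, 0.60) = 0.124 or P(X ≥ 16 | 22, 0.60) = 0.158. The documents do not support this, because it contradicts 8.2 and 8.5.

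**The response need not come before removal.** The rule does not say when it must occur, and 6.1.3 schedules an assessment 8-12 weeks after the last dose. True, but a response at that visit is still not the 12-month status, and the lack of a date remains.

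**Section 8.5.1 settles the denominator.** It is the section on the analysis population, its wording on a plain reading includes replaced patients, and the early-removal rule would be pointless if they were excluded. This also stands, so it would be wrong to say that the plan is silent on them. What remains is that the abstract, 3.2, 7.2.1.1 and 8.3.2 work with another set, and 7.2.1.1 cannot be put aside because the endpoint is itself a CR/PR classification.

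**One patient decides any exact test at its boundary.** Correct. The example shows sensitivity to the reading; it is not evidence that bias has occurred.

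**Conclusion.** The concern holds in a limited form and should be fixed. The early-removal rule does not do the cautious job claimed for it, because an undated response lifts it. The plan states no result for a missing 12-month assessment or for off-protocol treatment without local progression. The population on which N = 24 and 81% power rest is not the population that 8.5.1 analyses.

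Upward bias is possible, not shown. It arises if the evaluable-set reading is used and replaced failures drop out, or if patients without a stated result are omitted or scored as controlled. With one replaced failure assumed, the difference is 75.0% against 72.0%, and p = 0.096 against 0.154. The stated sample size and power are correct for 24 patients. Confidence is medium, because the size depends on exit counts that the documents do not give.

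**What to change.** **Sections 8.5 and 8.5.1.** Replace the early-removal sentence, dropping the documented-response exemption, with: success is CR or PR without PD in the PTV, documented at the 12-month assessment; every other patient who started concurrent therapy is a failure in the primary analysis, including early removals without that documentation and patients whose 12-month assessment is missing. Count salvage surgery or other non-protocol treatment to the treated site as failure. A patient who stopped radiation early but has documented control at 12 months is then a success.

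**Sensitivity analyses.** Vary the handling of death without local progression, of unknown status, and of an off-protocol Hedgehog inhibitor or chemotherapy given without local progression. These are choices: 6.1.5 keeps patients with metastatic disease in follow-up for local-regional control, so calling systemic treatment for distant disease a local failure would alter the endpoint.

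**Denominator.** State in the abstract, 3.2, 7.2.1.1 and 8.3.2 that replaced patients who started concurrent therapy stay in the 8.5.1 primary set. Reconcile 7.2.1.1, which calls induction progressors evaluable, with 8.5.1, which leaves them out because they never start concurrent therapy; report them as failures in a sensitivity analysis. Use the exact cut-off for the actual N: 18/24, 19/25 or 20/26.

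**Cost.** A few sentences of text, a less favourable estimate, and lower power if exits occur: 0.695 with one forced failure and 0.543 with two at N = 24. With one forced failure, about 30 patients would bring power back to near 0.80: cut-off 22/30, alpha P(X ≥ 22 | 30, 0.60) = 0.094, power P(X ≥ 22 | 29, 0.80) = 0.790.

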2.3.2 Secondary Endpoints

- Estimate of the probability of PFS, with failure defined as any disease recurrence or death due to any cause, and OS with each duration measured from the time of first treatment with vismodegib to 12 months after completion of study treatment.
- The number and attribution of all adverse events, (including vital signs, physical findings, and clinical laboratory results, CTCAE, v 4.0) in patients who receive any amount of study drug and radiation therapy at any point during protocol therapy or during the followup period.
- The proportion of any adverse events (CTCAE, v. 4.0) assessed to be definitely, probably, or possibly related to vismodegib or its combination with radiation therapy at any point during protocol therapy or during the followup period.
- The proportion of patients experiencing Grade 4-5 adverse events assessed to be definitely, probably, or possibly related to the induction or concurrent treatment components of the protocol regimen (that is not definitely related to disease progression) at any point during protocol therapy or during the followup period.
- The proportion of patients discontinuing treatment due to toxicity during the concurrent administration of vismodegib and radiation therapy (<75% of planned radiation therapy delivered).
- Response rate (as per RECIST) of the primary site and regionally involved areas following all treatment components at 3 months after the completion of protocol therapy.

- Proportion of patients with a decrease of BCC within the irradiated planning tumor volumes (PTV) in patients who complete initial combined therapy, indicating a clinical response to vismodegib and radiation therapy.

3 Study Design

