The duration of overall CR is measured from the time measurement criteria are first met for CR until the first date that recurrent disease is objectively documented.

Duration of stable disease

Stable disease is measured from the start of the treatment until the criteria for progression are met, taking as reference the smallest measurements recorded since the treatment started.

Progression-Free Survival

Progression-free survival (PFS) is defined as the duration of time from start of treatment to time of progression or death due to any cause.

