8.2 Study Endpoints

Primary Endpoint:

- The proportion of patients with local-regional control at 12 months from protocol therapy completion, defined as complete or partial response, with absence of PD (see section 7.2) within the irradiated PTV.

Secondary Endpoints:

- Estimate of the probability of PFS and OS 12 months after protocol therapy completion. PFS is measured until disease recurrence or death due to any cause, whichever occurs first.
- Number and attribution of all adverse events (including vital signs, physical findings, and clinical laboratory results, CTCAE, v 4.0) in patients who receive any amount of study drug and radiation therapy.
- For each toxicity, the maximum occurring grade will be tabulated for each patient. The results will be summarized by toxicities observed during vismodegib treatment alone, during concurrent vismodegib with radiation therapy, for 3 months immediately following the completion of protocol therapy and for up to 12 months after completion of protocol therapy. The focus will be on the proportion of patients experiencing \geq grade 3 toxicity during each of these intervals.
- Proportion of patients experiencing Grade 4-5 adverse events assessed to be definitely, probably, or possibly related to the induction or concurrent treatment components of the protocol regimen (that is not definitely related to disease progression).
- Proportion of patients discontinuing treatment due to toxicity during the concurrent administration of vismodegib and radiation therapy. For this endpoint, discontinuation is defined as $<$ 75% of planned radiation therapy delivered.
- Response rate per RECIST criteria in patients who complete initial combined therapy of the primary site and regionally involved areas in subjects with measurable disease prior to initiation of therapy at 3 months after completion of protocol therapy.
- Proportion of patients with a decrease of BCC within the irradiated PTV after completing all protocol therapy to estimate clinical response to vismodegib and radiation therapy.

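### Read literally, the only timed PFS estimate in Section 8.5 falls about 5 months before the time point set in Sections 2.2, 2.3.2 and 8.2, and Section 8.5 gives OS no time point

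*Combined protocol and SAP*

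**What the plan says.** Three places fix the PFS and OS time point by reference to the end of therapy.

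- Section 8.2 lists the endpoint as: "Estimate of the probability of PFS and OS 12 months after protocol therapy completion".
- Section 2.3.2 says each duration is "measured from the time of first treatment with vismodegib to 12 months after completion of study treatment". Section 2.2 and the abstract say the same.

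Section 8.5, which holds the analysis rule, starts both clocks when protocol therapy starts. It plans Kaplan-Meier point estimates with confidence intervals and names, as an example beside the median, "percent PFS at 12 months". No origin other than the start of therapy is given for those 12 months, and no time is named for OS.

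On events, Section 8.2 says "PFS is measured until disease recurrence or death due to any cause, whichever occurs first", and Section 7.2.1.4 says "Progression-free survival (PFS) is defined as the duration of time from start of treatment to time of progression or death due to any cause". Section 8.5 puts both event definitions into one clause: "until death due to any cause or until the first evidence of any disease progression, or death, respectively".

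**The concern.** All these sections start the clock at first treatment. They differ on where the curve is read. Sections 2.2, 2.3.2 and 8.2 ask for the probability 12 months after therapy ends. Section 8.5, followed as written, gives the probability 12 months after therapy begins. The patient spends roughly 5 of those months on treatment, so the reading comes well before the endpoint and before the primary time point for local-regional control.

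An analyst who worked only from Section 8.5 would produce neither of the two estimates that Section 8.2 calls for: the PFS figure would be early and there would be no OS figure. A survival curve cannot rise, so the early PFS figure can only equal or exceed the one the endpoint describes. If the time is left open until the data are in, the more favourable figure could be reported with Section 8.5 as support.

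A smaller matter is the compressed event clause, which a reader has to decode from other sections.

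**Working it through.** **The plan's own figure.** The only power statement concerns the primary endpoint: 24 patients, 60% against 80%, one-sided 0.10, exact binomial (Section 8.3.1). Rejecting at 18 or more successes of 24 gives a type I error of 0.096 and power of 0.811, which reproduces the stated 81%. PFS and OS have no target rate or power, and nothing below touches this calculation.

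**Inputs for the time points.**

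- Treatment lasts 21 weeks in Section 8.1. At 365.25/12/7 = 4.35 weeks per month, this is 21/4.35 = 4.8 months.
- Treatment lasts about 5.5 months in Sections 8.3.1 and 8.4.
- The End of Treatment visit is at weeks 29-33 (Table 6.1). Follow-up visits are 3, 6 and 12 months after that visit (Section 6.1.4).

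**Step 1: both time points on the Section 8.5 clock.**

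| | 21 weeks of treatment | 5.5 months of treatment |
|---|---|---|
| Endpoint, months from first dose | 12 + 4.8 = 16.8 | 12 + 5.5 = 17.5 |
| 12 months from first dose, as months after therapy ends | 12 - 4.8 = 7.2 | 12 - 5.5 = 6.5 |
| Gap (months) | 4.8 | 5.5 |

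**Step 2: size of the difference.** The documents give no PFS rate for this regimen, so the rates below are assumed. With a constant hazard and S the true PFS at the endpoint time, the reading at 12 months from first dose is S^(12/16.8) or S^(12/17.5).

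| Assumed S | 21 weeks | 5.5 months |
|---|---|---|
| 0.60 | 0.695 (+9.5 points) | 0.704 (+10.4 points) |
| 0.70 | 0.775 (+7.5) | 0.783 (+8.3) |
| 0.80 | 0.853 (+5.3) | 0.858 (+5.8) |
| 0.90 | 0.928 (+2.8) | 0.930 (+3.0) |

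The range is about 3 to 10 points.

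**Step 3: which assessments each reading rests on.** Counting from the End of Treatment visit, the follow-up scans fall at about weeks 42-46, 55-59 and 81-85. Twelve months from first dose is week 52. Twelve months after a week-21 completion is week 73. After first dose, the week-52 reading therefore rests on the end-of-induction and End of Treatment assessments and the first follow-up visit. The week-73 reading adds only the 6-month visit. The final visit comes after both.

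**Step 4: the event clause.** It can be divided in two ways.

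- *First division.* PFS takes everything up to the last comma (death or first progression), and OS takes the closing words (death). This agrees with Sections 7.2.1.4 and 8.2.
- *Second division.* The two *until* phrases are matched in order to PFS and OS. PFS then ends at death, and OS ends at progression or death.

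**The case against.** The best defence is that the 12-month figure is introduced as an example, not as a fixed landmark. Elsewhere Section 8.5 uses 12 months to mean after treatment, so this may be shorthand for the time point in Section 8.2. That is plausible, and it means the documents do not show that the wrong rate will be reported. A reader might infer a settled decision to report the early rate, but the text does not go that far. What stands is that Section 8.5 anchors its local-regional control and 3-month response estimates explicitly to the end of therapy. It leaves PFS with no anchor except the start of therapy, and it omits OS.

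A reader might also infer that Section 8.5 swaps the PFS and OS events. The documents do not support this. The comma before the closing words permits the correct division, and Sections 7.2.1.4 and 8.2 define PFS correctly. The wording is awkward, no more.

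Nor are 5 months of follow-up lost. The Kaplan-Meier curve uses all the data and can be read at any later time. The issue is one reading from that curve.

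Finally, the size is hypothetical. Scheduled progression findings come in steps, and only one scheduled assessment separates weeks 52 and 73, so a smooth-hazard figure is a rough guide. This is correct. The direction does not depend on the hazard, but the 3 to 10 points do.

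**Conclusion.** The concern holds as a conflict over the reading time, together with a missing OS time point and an ambiguous event clause. Taken literally, Section 8.5 reads PFS 4.8 to 5.5 months before the endpoint in Sections 2.2, 2.3.2 and 8.2. That reading cannot be lower than the endpoint rate. The excess of about 3 to 10 points assumes a constant hazard and a true PFS of 60% to 90%, and it could be nil if no events are recorded between the two times.

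The documents do not settle the endpoint to the week. The treatment duration is given two ways, and the last scheduled assessment falls later than either version of the endpoint time. PFS and OS are descriptive secondary endpoints with no test attached, so the sample size and primary analysis stand. The change should be made, but the trial does not depend on it.

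**What to change.** Replace the compressed passage in Section 8.5 with separate statements:

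1. PFS runs from the first vismodegib dose to the first progression or recurrence, or death from any cause, whichever comes first.
2. OS runs from the first vismodegib dose to death from any cause.
3. Kaplan-Meier estimates of PFS and OS, with 95% confidence intervals, are reported at one pre-specified time from first dose that represents 12 months after planned completion of therapy. About 17 months fits the documents' figures of 16.8 and 17.5. State which planned treatment duration the chosen time uses.
4. The estimate at 12 months from first dose is supplementary and labelled as such.

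Add a note that follow-up visits are counted from the End of Treatment visit, so the last scheduled assessment is at about weeks 81-85. Progression first found there falls after the reported time.

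The same curves supply every estimate, so no new visits, data or patients are needed. The only cost is a possibly less favourable percentage.
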